### **11.3 Risk associated with Breast MRI**

The Magnetic Resonance Imaging protocols utilized in this study use standard magnetic fields and do not involve contrast reagents. Thus there are no known risks to the participants from the imaging protocols. However, patients with claustrophobia or electrically, magnetically, or mechanically activated implants (pacemakers, cochlear implants, etc.) are ineligible secondary to the increased risks from imaging inherent with their participation.

## **12 Information on Breast Biopsy Procedures and Risks.**

During the study, participants on sulindac will be asked to provide a breast biopsy (optional) at baseline 2 and at 6 months on sulindac and all participants will undergo non-contrast, magnetic resonance imaging of the breast at various time points. These procedures and their risks are described below.

### **12.1 Breast Biopsy Procedure (sulindac intervention study only)**

All participants **receiving sulindac** will be asked to provide an optional core needle biopsy at baseline and 6 months from the contralateral, unaffected breast; we estimate that ~75% will agree to the first and 60% to the second request, yielding approximately 40 participants with both baseline and 6-month biopsies. For participants who consent to breast biopsy at baseline, the breast specialist (radiologist or surgeon), as a fee for service, will use mammography images to identify two areas of increased radiographic density, located at least 2 cm apart, in the upper, outer quadrant of the contralateral (uninvolved) breast. Mammographically dense areas will be co-localized with ultrasound guidance, with their relative positions recorded by clock-face and linear distance away from the nipple. Under ultrasound guidance, an 14-gauge needle will be used to obtain 8 tissue cores from one of the two identified high-density areas. Since 5-10 cores are typically obtained during clinically indicated biopsy procedures, our tissue sampling protocol should not impose undue participant burden or risk. Representative FFPE specimens will be reviewed separately by Arizona's University Medical Center pathology department (required) for UACC site and Stony Brook University pathology department for SBCC site.

### **12.2 Methods for tissue biomarkers.**

We estimated that 25% of subjects (n = 40) will consent to serial core biopsy procedures of the contralateral, unaffected breast at baseline and 6 months, allowing us to explore the effect of AI and AI+sulindac on molecular markers in normal tissue. To date, the response rate is 90% for initial biopsy and 75% for second biopsy.

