All the secondary aims are exploratory in nature. For biomarker related aims, the minimum sample size is expected to be 40 to compare changes in the breast tissue in women consenting to serial biopsy. Forty women will allow us to detect a standardized difference of 0.45 SD units with 80% power (assuming a two-sided  $\alpha$  of 0.05). Justification of the sample size is similar to that for the primary endpoints outlined above. To determine the detectable increase in MAP, we assume a simplified design in which the difference between the average value during sulindac treatment and baseline will be compared. We will have 80% statistical power to detect a 4 mm Hg increase in MAP in women while on sulindac versus baseline (one-sided test). This estimate is based on the SD of 13 mm Hg observed in a recent study of middle-aged women referenced in the funded grant submission, which demonstrated an adjusted hazard ratio of 1.43 for incidence of CVD death for a 1-SD increase in MAP.

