In consultation with NCI, concern was raised that prior studies of AIs showing no effects of AIs on BD were based on mammography and not the more sensitive MRI method under investigation. As such, an observational (non-randomized) control group comprised of BC patients stable on an AI was included specifically to monitor for AI effect on BD using the MRD method.

Initially, the target sample size was reduced to 75 and 60 in the intervention and observation groups, respectively. A previously planned futility analysis of SUL effect on MRD after 40 participants completed 12 months of intervention was changed to the primary analysis on limited resources and slow accrual. Patients consented to banking tissue biopsies for future biomarker studies.

Modified Study Hypotheses: Because of the modification to the study design, the study hypotheses were modified as follows:

Primary

SUL 150 mg BID for 12 months will decrease MRD in postmenopausal women taking aromatase inhibitor therapy.

- a. As a sensitivity analysis of this primary hypothesis, per-study analysis described below will also be performed using only subjects who are adherent with study protocols (adherence is defined as having taken at least 80% of study agent).
- b. As a sensitivity analysis of this primary hypothesis, per-study analysis for primary hypothesis will also be performed using only those subjects with baseline BD $\geq 15\%$.

Secondary

SUL 150 mg BID for 12 months will be well tolerated and grade 3 adverse events will not exceed 10% and patients who drop out secondary to adverse events will not exceed 10%. *With low sample size of 40, only when there are no grade 3 AE or drop out secondary to AEs, can say it will not exceed 10% (point estimate is 0% with 95% Blyth-Casella-Still CI (0-7.78%).*

Reportable Outcomes

1. Change in BD from baseline at 6 and 12 months by MRD in postmenopausal women receiving AI for treatment of breast cancer and 95% confidence interval will be reported separately for:
 - a. participants in the sulindac group who started sulindac and who had at least one MRD measure on intervention,
 - b. participants enrolled and started in the observation arm with at least one MRD measure post baseline,
 - c. participants adherent to SUL intervention (same caveats as a), and

- d. in both arms but reported separately for participants with baseline BD $\geq 15\%$ (same respective caveats as a and b).

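### The 40 paired biopsies behind the tissue power statement are mislabelled as 25% of subjects and do not carry over to the SAP's reduced sulindac group

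*Protocol*

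**What the plan says.** Two protocol sections describe how many women will give both biopsies.

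- Section 12.1, which applies to the sulindac study only: "we estimate that ~75% will agree to the first and 60% to the second request, yielding approximately 40 participants" with both the baseline and the 6-month sample.
- Section 12.2: "We estimated that 25% of subjects (n = 40) will consent to serial core biopsy procedures". The next sentence reports experience so far: "To date, the response rate is 90% for initial biopsy and 75% for second biopsy". No denominator is given.

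Section 27.4 builds on the 40. It says that "the minimum sample size is expected to be 40 to compare changes in the breast tissue in women consenting to serial biopsy", and then: "Forty women will allow us to detect a standardized difference of 0.45 SD units with 80% power", at a two-sided 0.05 level.

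The SAP changes the size of the trial. It first lowers the intervention target to 75, and then, citing limited resources and slow accrual, reports: "A previously planned futility analysis of SUL effect on MRD after 40 participants completed 12 months of intervention was changed to the primary analysis". Its secondary hypothesis describes the sulindac group as a low sample of 40 when it judges adverse event rates. The SAP drops the planned tissue biomarker studies. It adds an exploratory aim on collagen alignment in the biopsies and makes the biopsy acceptance proportions a reportable outcome. It restates neither a number of pairs nor a tissue power.

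**The concern.** The percentage and the count in Section 12.2 cannot both be right for an arm of 100, and the percentage conflicts with Section 12.1. More important, the protocol's only statement of tissue sample size and power was written for a sulindac arm of 100, while the SAP describes one of about 40. The current protocol text is later than the SAP (it refers to January 2021, the SAP to November 2019), yet it still calls 40 pairs a minimum. Section 28.5 still plans proliferation, protein expression and transcriptomic measures on the tissue. A reader weighing a null tissue result has only Section 27.4 to turn to, and could credit the comparison with more sensitivity than the reduced group provides.

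**Working it through.** **Inputs.** Sulindac arm 100 women, 90% reaching the intervention phase, 80 evaluable at 12 months (protocol Section 8). Planned acceptance 75% then 60% (12.1). Observed acceptance 90% then 75% (12.2). Effect 0.45 SD, two-sided 0.05, 80% power (27.4). Analysis after 40 completers (SAP). The second rate is taken as conditional on the first.

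**1. The 25% label.** 0.25 × 100 = 25; 0.25 × 90 = 22.5. Section 12.3 loosely mentions all participants, but 0.25 × 175 = 43.75. Forty is 25% only of 40 / 0.25 = 160, a denominator found nowhere in the documents.

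**2. Where the 40 comes from.** 100 × 0.90 × 0.75 × 0.60 = 40.5 pairs. This is an expected value rather than a minimum: on 80 completers the same rates give 80 × 0.45 = 36.

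**3. The plan's power figure.** For a paired t test, power is the probability that a noncentral t with n − 1 degrees of freedom and noncentrality 0.45√n exceeds the two-sided 5% critical value.
- n = 40: 79.3%, detectable difference 0.454 SD.
- Normal approximation: Φ(0.45√40 − 1.960) = Φ(0.886) = 81%.
- Required n: ((1.960 + 0.842) / 0.45)² = 38.8, so 39 by the normal approximation; 41 by the t test.

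The stated figure reproduces.

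**4. Observed rates at the protocol's size.** 90 × 0.90 × 0.75 = 60.75 pairs; 93% power at 61.

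**5. The SAP's size.** The SAP does not say how many women started sulindac. As a range, take 40 (no loss) to 45 (the protocol's own attrition: 40 × 90/80 = 45).

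| Rates | Starters | Pairs | Power for 0.45 SD | Detectable at 80% power |
|---|---|---|---|---|
| Observed, 0.90 × 0.75 = 0.675 | 40 | 27.0 | 61% | 0.56 SD |
| Observed | 45 | 30.4 (30 used) | 66% | 0.53 SD |
| Planned, 0.75 × 0.60 = 0.45 | 40 | 18.0 | 44% | 0.70 SD |
| Planned | 45 | 20.3 (20 used) | 48% | 0.66 SD |

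If the observed 75% is instead a share of all starters, 45 women give 0.75 × 45 = 33.75 pairs; 34 pairs give 72% power and 0.50 SD.

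**6. What 40 pairs would need.** 40 / 0.675 = 59.3, about 59 starters at the observed rates; 40 / 0.45 = 88.9, about 89 at the planned rates.

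**The case against.** The strongest reply is that the 25% is one stale percentage with no effect on the power statement. At the protocol's size that is correct. A reader might infer from Section 12.2 that only 25 pairs were to be expected and that power was 58%. The documents do not support this: Section 12.1 with Section 8 gives 40.5 pairs, the power reproduces, and the observed rates would give about 61 pairs.

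A second reply is that 40 completers at 12 months is the wrong base. The second biopsy falls at 6 months on drug, so women who stopped later, or had not yet finished, can still contribute a pair. Section 27.3 projected about 90 women with 9-month study measures, and about 100 started, by the time 40 reached 15 months. The SAP's interim target of 75 would give 75 × 0.675 = 50.6 pairs at the observed rates. This stands in part, and is why the 40 to 45 starters are an assumption. But the Section 27.3 projection assumes 5 participants a month, while the SAP reports slow accrual and itself works with a group of 40. Even 75 starters give only 75 × 0.45 = 33.75 pairs at the planned rates.

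Third, the stakes are low. Section 27.4 calls these aims exploratory and the SAP dropped the planned tissue studies. A reader might also infer that the collagen aim rests on the 80% power. It does not: the SAP states no size or power for it. Nor does either document say that a null tissue result would exclude 0.45 SD. This objection stands and sets the severity.

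**Conclusion.** Minor. Two things hold. The 25% in Section 12.2 is arithmetically wrong for the arm in which biopsies are offered, and it conflicts with Section 12.1. And Section 27.4's 40 pairs with 80% power for 0.45 SD, sound for the arm of 100, is not supported at the size the SAP describes. With 40 to 45 starters, expected pairs run from 18 to 30, power from 44% to 66%, and the detectable difference from 0.70 down to 0.53 SD. These figures rest on the assumed number of starters and on the second acceptance rate being conditional on the first. The alternative reading of the observed 75% still leaves power at about 72%. If about 59 or more women started and the observed rates held, the shortfall would disappear. The documents do not show that they did.

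**What to change.** In Section 12.2, delete the statement that 25% of subjects equals 40. In Sections 12.1 and 12.2, give one serial-biopsy rate with its numerator and denominator, the denominator being women who started sulindac, and say whether the second rate is conditional on the first.

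In Section 27.4, replace the minimum of 40 and the 0.45 SD with the actual number of paired biopsies at the SAP's size. That number can be counted, since Section 20 records that all tissue had been collected by January 2021. State the matching detectable difference, worked out from the number of pairs alone and not from the observed effect, and label it exploratory. For reference, at 80% power it is 0.66 SD for 20 pairs, 0.58 for 25, 0.53 for 30, 0.50 for 34 and 0.45 for 40.

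The cost is wording only: no further patients, biopsies or analyses. The stated sensitivity may become less favourable.

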### *12.2.1 Histological characterization of tissue from core biopsy*

The baseline and 6 months' breast biopsy specimen obtained will be microscopically examined. The proportion of the specimen occupied by fat, epithelium, and collagen will be estimated. The presence or absence of major and medium-sized ducts will be noted; if present, the ducts will be classified as normal, distended with secretion, or showing periductal fibrosis. Lobules will be classified as well developed, sclerotic, or atrophic.

### *12.2.2 Laboratory assays*

All breast tissue markers will be analyzed at AZCC ([name] lab). Uncontrolled proliferation and decreased apoptosis are among the hallmark features of cancers. As an exploratory aim, we propose to evaluate the effect of 6-month exposure to AI+sulindac on proliferation (cyclin B1 and Ki67), apoptosis (cleaved caspase 3), and pro-apoptotic/anti-growth markers (i.e., GDF15 and p21) in the subjects that agree to core biopsy. These data will also be available to conduct cross-sectional analyses relating their levels to MRI-derived features of the breast to gain insight on the relationship between breast density and/or diffusion and proliferation/apoptosis indices.

### *12.2.3 Immunohistochemistry (IHC) for measures of proliferation and apoptosis*

For direct quantitative tissue measures of proliferation and apoptosis, we will measure Ki67 expression for proliferation by IHC and cleaved caspase 3 as an indicator of apoptotic activity in normal breast tissue from high-risk women. For Ki67, we use the DAKO MIB1 antibody diluted 1:100 under diagnostically validated conditions using the Discovery XT Automated IHC system (Ventana Medical Systems) and analysis with the Aperio ScanScope™ system. The Aperio system includes a suite of automated Ki67-specific image analysis algorithms that have been FDA-cleared for in vitro diagnostic purposes. For each FFPE stained section, the Ki67 analysis algorithm tool provides measures for % positive nuclei and intensity score. To illustrate performance of the scoring algorithm and to show the range of Ki67 expression, we analyzed 10 random fields for each of 12 core biopsy from the unaffected breast of 12 patients in an unrelated study. Only ductal epithelial cells were selected for each random field. Scans are repeated 3 times, each time reselecting a random set of 10 fields. The mean number of total nuclei counted per scan was 3900. The between-scan variation (sum across 10 random regions) or inter-scan coefficient of variation (CV) was 3.52%, demonstrating a highly reproducible estimate of Ki67 expression.

Unlike proliferation, the study of apoptosis in normal, but high-risk, breast tissue and induction by pharmacologics is limited. The few studies that measured DNA fragmentation by the TUNEL assay have reported on apoptotic response to drug in tumor, not normal tissue. Because the TUNEL assay

conducted on FFPE is prone to high CVs, we have elected to measure cleaved caspase 3 since caspase induction has been reported to be induced by sulindac(90). Caspase 3 has been applied in the study of normal (not tumor) breast tissue response to long-term HT in cynomolgus monkeys wherein the untreated control group showed a mean 10.7% basal staining and similar, though slightly higher, Ki67 values (8.4%) to normal human breast (Conner et al. 2005). We will score caspase 3 in a manner analogous to Ki67 described above.

#### *12.2.4 Alternative measure of tissue response to sulindac*

Sulindac exhibits both COX-dependent and -independent actions with activity reported for a number of targets that include evidence for inhibition of cyclic-GMP phosphodiesterase resulting in increases in protein kinase G and subsequent induction of caspase (Haanen 2001). In addition, a number of studies find evidence for effects on GDF15, p21, cyclin D1,  $\beta$ -catenin, PPAR $\gamma$ , MMP-1, PI3KR1, uPA and a number of other molecules (Kim et al. 2005; Greenspan et al. 2010). Thus, because of the broad spectrum effects, we propose to conduct exploratory analyses comparing change in gene expression patterns at the tissue level, pre- and post-drug, using the Illumina DASL platform for high-density expression profiling. The DASL requires as little as 200 ng input RNA and performs in formalin fixed paraffin embedded tissue derived RNA. Expression profiling will be performed under contract as fee-for-service at Illumina (San Diego, CA). Given the small sample size, we will explore gene expression changes by assignment to placebo or sulindac and confirm positive findings with Q-RTPCR and interpret with caution. The work will be conducted in collaboration with the Informatics/Bioinformatics Shared Services of the AZCC Core Grant led by Drs. [name] and [name] who are experts in the field of gene expression profiling (<http://www.azcc.arizona.edu/research/shared-services/biss>) and who have previously published with PI [name] (Egan et al. 2010; Flowers et al. 2010), including results from a study showing mammary tumor changes in gene expression following exposure to conjugated linoleic acid (Flowers et al. 2010).

### **12.3 Risk associated with Breast Biopsy**

A breast biopsy procedure will be offered to all participants as an optional procedure. Potential risks associated with biopsy include: bleeding/bruising/hematoma formation at the biopsy site, pain at the site, rare instances of infection, and a small scar at the site. The risk of significant bleeding complications requiring surgery or hospitalization is nil. However, there is a 30% risk of hematoma or bruising after breast biopsy that spontaneously resolves.

## **13 MEASURES OF PAIN IN CLINICAL TRIALS**

Results from a recent study of 1147 cancer patients from the Eastern Cooperative Oncology Group suggest that measurement of past-week worst pain with the BPI-SF had the strongest relationship with pain interference scores, supporting its use as a primary endpoint measure for clinical trials in patients with persistent pain (Shi et al. 2009). Thus, to assess the severity of pain and to measure change in pain with treatment, participants in this study will be administered the BPI-SF at baselines and 3, 6, 9, and 12 months (baseline, 6 and 12 months for AI only arm) to rate their pain at its worst, least, and average during the past 24 hours using the BPI-SF developed for clinical trials by [name] (Mendoza et al. 2006; Keller et al. 2004; Dworkin et al. 2010; Cleeland and Ryan 1994). The BPI-SF is a one-page form that provides patients with simple language with which to communicate about their pain using a simple numeric rating system. The BPI-SF asks patients to rate their pain at its worst, least, and average during the past 24 hours with each item rated on a 0-10 scale, with 0 indicating 'no pain' and 10 indicating 'pain as bad as you can imagine' (copy of instrument is provided in Appendix 1). The BPI-SF also rates, for exploratory analyses, how much the pain interferes with general activity, mood, walking ability, normal work, relations with other people, sleep, and enjoyment of life on a scale of 0 to 10, with 0 indicating 'does not interfere' and 10 indicating 'completely interferes'. The primary pain-related endpoint for our study will be 12-month change in the past 24 hours' worst pain score. Past 24 hours' average and past 24 hours' least pain scores will be included as secondary pain-related study endpoints.

In addition, we will administer the WOMAC, a 24-item instrument developed to assess pain, stiffness, and physical function in participants with hip and/or knee osteoarthritis (Wolfe and Kong 1999). This instrument is well validated (Wolfe and Kong 1999) and has been modified from its original form and used extensively to examine specific joint pain changes following treatment, including drug-based interventions for back pain, rheumatoid arthritis, and fibromyalgia (Rothenfluh et al. 2008). For our study, we will use the 5-point Likert-type format.

## **14 INFORMATION ON PLASMA AND URINARY BIOMARKER PROCEDURES AND RISKS**

### **14.1 Urine Sample Collection, Processing and Analyses**

For the sulindac treated group, urine will be collected at both Baseline visits and at 3, 6, 9, 12 month visits. For the observational group, urine will be collected at baseline and at 6 and 12 month visits. All urine samples will be aliquoted in clinic the same day as collection and transported to the Cancer Prevention & Control (CPC) laboratory at the University of Arizona Cancer Center or to the [name] Laboratory in the Department of Pathology within 2 hours for storage at -80°C for future analyses. All urine specimens are labeled and tracked with a unique sample ID. The CPC research lab and the [name] laboratory have Standard Operating Procedures in place established by [name] in

both sites and follow all regulations pertaining to lab safety, sample processing, specimen classification and repository management.

## **14.2 Blood Sample Collection, Processing and Analyses.**

### *14.2.1 Clinical Blood Chemistry Monitoring*

Blood will be collected when enrollment is initiated following consent, at baseline visits (post-washout and post-observation) and at 6, and 12 month on sulindac visits for sulindac treated group only. CBC with differential and platelet count, chemistry panel (biochemical profile) will be performed for the active arm (sulindac) only. The chemistry panel and CBC with differential are performed by a fee for service laboratory (Sonora Quest Laboratories in Arizona and Stony Brook Laboratories in Stony Brook New York). These service laboratories hold current accreditation issued by the College of American Pathologists' Laboratory Accreditation Program. Hard copies of the laboratory results are sent directly to the clinic on a routine basis. The study nurse will be responsible for noting any values for tests used in eligibility that are outside normal ranges and alerting the participant of these values.

### *14.2.2 Blood Banking*

For the sulindac treated group, blood will be collected at Baseline visits (post-washout and post-observation) and at 3, 6, 9, 12 month visits. For the observational group, blood will be collected at Baseline visit and at 6 and 12 month visits. Whole blood will be collected only once during the study at the first Baseline visit. Serum for banking will be collected in a Red top Vacutainer. Plasma for banking will be collected in a Lavender top EDTA Vacutainer. Whole blood will be collected from the same Lavender top EDTA Vacutainer as serum. Vacutainer tubes are centrifuged in the clinic the same day as collection. All blood specimens are labeled and tracked with a unique sample ID. Blood samples will be processed to serum and plasma and transported to the CPC (AZ) or [name] laboratory (Stony Brook NY) within 2 hours for storage in aliquots at -80°C for future analysis. At this time (January 2021), all blood samples have been collected, processed and stored as specified in the protocol. These samples will be relocated from the [name] laboratory to the Cancer Center Tissue Biobank until approved for sharing with the [name] laboratory at Cedars Sinai Medical Center under a Material Transfer Agreement. Only sample needed to complete agreed biomarker studies will be shared and all residual material returned to long term storage at either UACC or Stony Brook University.

[figure not shown]
